## **11.0 TOXICITIES/SIDE EFFECTS**

All toxicities will be rated as per the NCI Common Toxicity Criteria, with the exception of skin or nail related toxicities, which will be graded using CTC version 3.0 with modifications (see appendix B). Hepatic enzyme toxicities will also be captured according to the schema on page 30 as well (see FUDR Dose Modifications and Table I).

### **11.1 Toxicity Related to Chemotherapy**

- 11.1.1 FUDR: gastritis, gastroduodenal ulcers, chemical hepatitis, sclerosing cholangitis with jaundice, pruritus, diarrhea.
- 11.1.2 Dexamethasone: sodium retention, fluid retention, hypertension, development of cushingoid state, secondary adrenocortical and pituitary hypo-responsiveness, decreased carbohydrate tolerance, manifestations of latent diabetes.
- 11.1.3 Systemic Chemotherapy (CPT-11, 5FU/LV): diarrhea, myelosuppression, nausea, vomiting, stomatitis, neurotoxicity; neutropenia, thrombocytopenia, cumulative asthenia (CPT-11).

### **11.2 Toxicity Related to Panitumumab**

Toxicities will be recorded as adverse events on the Adverse Event case report form and must be graded using The National Cancer Institute's Common Toxicity Criteria (CTC) version 4.0.

Dermatologic Toxicity: Dermatologic toxicities occurred in 89% of patients and were severe (NCI-CTC grade 3 and higher) in 12% of patients receiving Panitumumab monotherapy. The clinical symptoms include, but are not limited to, dermatitis acneiform, pruritus, erythema, rash, skin exfoliation, paronychia, dry skin, and skin fissures. In some cases, it may cause infected sores requiring medical and/or surgical treatment, or cause severe skin infections that could be fatal. Subsequent to the development of severe dermatologic toxicities, infectious complications, including sepsis, septic death, and abscesses requiring incisions and drainage were reported.

Infusion Reactions: Severe infusion reactions included anaphylactic reactions, bronchospasm, and hypotension, which occurred in approximately 1% of patients.

Pulmonary fibrosis: In patients enrolled in clinical studies of Panitumumab, pulmonary fibrosis occurred in less than 1% (2/1467). Patients with a history of interstitial pneumonitis, pulmonary fibrosis, evidence of interstitial pneumonitis, or pulmonary fibrosis were excluded from clinical studies. Therefore, the probability of risk in a general population is uncertain.

**Electrolyte Depletion/Monitoring:** In patients enrolled in a clinical trial, 2% experienced hypomagnesemia (NCI-CTC grade 3 or 4), which required oral or IV electrolyte repletion. Hypomagnesemia occurred 6 weeks or longer after the initiation of Panitumumab. In some patients, both hypomagnesemia and hypocalcemia occurred.

**Photosensitivity:** Exposure to sunlight can worsen dermatologic toxicity. It is recommended that patients wear sunscreen and hats and limit sun exposure while receiving Panitumumab.

**Dermatologic, Mucosal, and Ocular Toxicity:** Ocular toxicities occurred in 15% of patients and included, but were not limited to: conjunctivitis (4%), ocular hyperemia (3%), increased lacrimation (2%), and eye/eyelid irritation (1%). Stomatitis (7%) and oral mucositis (6%) were reported. One patient experienced an NCI-CTC grade 3 event of mucosal inflammation. The incidence of paronychia was 25% and was severe in 2% of patients. Nail disorders were observed in 9% of patients.

**Other adverse effects include:** nausea, vomiting, mouth irritation, fever, headache, cough, shortness of breath, diarrhea (sometimes causing severe dehydration), abdominal pain, constipation, swelling of the hands and feet, and fatigue/weakness, hair loss, a decrease in magnesium, calcium and potassium levels in the blood, nose dryness or bleeding, increased growth of eyelashes and excessive hair growth.

The following adverse are rare but serious: blood clots in legs and lungs, stroke, acute kidney failure, lung complications, heart attack, shortness of breath, and septic death.

**Pregnancy:** Adequate contraception in both males and females must be used while receiving Panitumumab and for 6 months after the last dose of Panitumumab therapy.

**Pre-medication for Panitumumab:** Panitumumab specific pre-medication is not required for routine panitumumab infusions. If, during or after any infusion, a reaction occurs, pre-medication may be used for subsequent panitumumab infusions (e.g., acetaminophen/paracetemol and/or an H1 blocker, e.g., diphenhydramine).

**Interruption of Panitumumab Infusion:** Subjects who experience any serious infusion reaction during panitumumab administration will have the infusion stopped. Continuation of dosing will be based on the severity and resolution of the event. Suspected infusion reactions should be reported as an adverse event. All subjects who experience such an event will be followed for safety.

**Pre-emptive Management of Panitumumab Associated Skin Toxicities:** Clinical trial data indicate that integument and eye toxicities associated with panitumumab therapy are consistent with what has been observed for other EGFr inhibitors. Most integument- and eye-related toxicity events were mild or moderate in intensity.

**Pre-emptive treatment for skin toxicity includes (recommended):**

- Sunscreen SPF>30 when going outside
- Topical steroid (0.05% alclometasone cream) twice daily on face, chest and upper back
- Prophylactic use of alcohol-free emollient creams or ointments to combat dryness
- Doxycycline 100mg twice daily or Minocycline 100 mg tabs 1 tab daily

The optimal duration of pre-emptive skin treatment is 6 weeks from panitumumab initiation. Subjects who subsequently experience skin toxicities  $\geq$  grade 2 may discontinue the pre-

emptive skin treatment, and their symptoms should be managed appropriately according to the institution's standard procedures.

### 11.3 Toxicity Related to the Pump and Catheters

Infection, hepatic artery thrombosis, pump malfunction, catheter occlusion, intra-abdominal bleed. The rate of pump failure is less than 1 percent. Patients will receive standard systemic therapy if the pump is unusable.

### 11.4 Dose Modifications

#### 11.4.1 Irinotecan, 5FU, Leucovorin Dose Modifications

- If patients have delays in treatments due to hospitalization or other reasons, they should proceed with treatment as scheduled.
- Patients who experience grade 3 or 4 toxicity may continue treatment at a lower dosage level once toxicities have fully resolved (refer to tables below). Toxicity should resolve within two weeks. If the physician feels the patient cannot tolerate systemic therapy, they can hold therapy for one week. If the patient has elevated liver function tests in the PI's discretion, systemic therapy can be held and Decadron can be placed in the pump with heparin saline.
- Guidelines for re-starting medication are listed in table below:

Dose Reduction for Hematologic Toxicities: Irinotecan + 5FU + LV (mg/m^2/day)

Grade	Toxicity	Irinotecan	5FU Infusion	Leucovorin
3	Neutropenia	20% decrease	20% decrease	20% decrease
4	Neutropenia	30% decrease	30% decrease	30% decrease
3	Febrile neutropenia a	20% decrease	20% decrease	20% decrease
4	Febrile neutropenia a	30% decrease	30% decrease	30% decrease
3	Thrombocytopenia	20% decrease	20% decrease	20% decrease
4	Thrombocytopenia	30% decrease	30% decrease	30% decrease

aFebrile Neutropenia = ANC < 1.0 x 10^9/L with fever ≥ 38.5° C

Dose Reductions for Non-Hematologic Toxicities: Irinotecan + 5FU + LV (mg/m^2/day)

Grade	Toxicity	Irinotecan	5FU Infusion	Leucovorin
3	Nausea and/or vomiting despite premedication with an effective antiemetic therapy	20% decrease	20% decrease	20% decrease
3	Diarrhea despite premedication with an effective antidiarrheal therapy	20% decrease	20% decrease	20% decrease
4	Nausea and/or vomiting despite premedication with an effective antiemetic therapy	30% decrease	30% decrease	30% decrease
4	Diarrhea despite premedication with an effective antidiarrheal therapy	30% decrease	30% decrease	30% decrease

3	Stomatitis	No dose reduction	20% decrease	20% decrease
4	Stomatitis	No dose reduction	30% decrease	30% decrease
$\geq 2$	Cardiac toxicity	No dose reduction	Stop treatment	Stop treatment
3 or 4	Hand/Foot Skin reaction	No dose reduction	20% decrease	20% decrease

#### 11.4.2 FUDR Dose Modifications

—Reference value is defined as the value obtained on the first day of the most recent FUDR dose.

To determine if a FUDR dose modification is necessary, compare reference value to the either the value obtained on the day pump was emptied (e.g. day 14) or the value obtained on the day of planned pump filling (e.g. day 28), whichever is higher. Percentages listed under —FUDR Dose refer to percentage of last dose of FUDR administered.

**TABLE I: FUDR DOSE MODIFICATION SCHEMA:**

	Reference Value*	% FUDR dose
SGOT (at pump emptying or day of planned retreatment, whichever is higher)	0 to $< 2 \times$ reference value	100%
	2 to $< 3 \times$ reference value	80%
	3 to $< 4 \times$ reference value	50%
	$> 4 \times$ reference value	Hold A
ALK PHOS (at pump emptying or day of planned retreatment, whichever is higher)	0 to $< 1.2 \times$ reference value	100%
	1.2 to $< 1.5 \times$ reference value	50%
	$> 1.5 \times$ reference value	Hold B
TOT BILI (at pump emptying or day of planned retreatment, whichever is higher)	0 to $< 1.2 \times$ reference value	100%
	1.2 to $< 1.5 \times$ reference value	50%
	$> 1.5 \times$ reference value	Hold C
If SGOT $> 4 \times$ reference value, alkaline phosphatase $> 1.5 \times$ reference value, total bilirubin $> 1.5 \times$ reference value, then treatment will be held and will not be reinstated until values come down to more normal levels, as indicated in section —Recommencing FUDR Treatment After Hold.		
A SGOT elevation, B Alkaline Phosphatase elevation, C Total bilirubin elevation		

\* If patient's Alkaline Phosphatase or T Bili shows a continual rise from Day 1 of treatment, then the Day 1 value will be used as the reference value for that patient when determining whether to hold treatment, and time of re-treatment after hold.

#### RECOMMENCING TREATMENT AFTER HOLD

Reason for treatment delay	Chemotherapy resumed when value has returned to:	% FUDR dose
----------------------------	--	-------------

SGOT elevation	3 X reference value	25% of last dose
Alkaline Phosphatase elevation	1.2 X reference value	25% of last dose
Total bilirubin elevation	1.2 X reference value	25% of last dose

- If patient develops a total bilirubin  $\geq$  3.0 mg/dl, the pump should be emptied and Dex 25 mg plus heparin 30,000 u and saline 30 cc placed in the pump q 14 days. Once there is no longer evidence of toxicity, Dex dose should be tapered in increments of 5 mg every 14 days. Tapering will continue unless enzymes increase. FUDR should be permanently discontinued unless there is evidence of disease progression (increasing CEA, worsening CT scan, worsening clinical status) AND bilirubin has returned to  $\leq$  1.5 mg/dl. In this case, FUDR can be restarted as follows: Use 25% of the last FUDR dose given with Dex, heparin and saline in the pump for 7 days. Pump should be emptied after 7 days, and patients given a 3-week rest period. This treatment and treatment schedule should continue as long as bilirubin remains  $\leq$  1.5 mg/dl and liver enzyme values do not increase.
- If a patient presents with abdominal pain, HAI FUDR should not be given and, if the pump is already filled with FUDR, then the FUDR should be emptied immediately. Epigastric pain unresponsive to oral H2 blocker use is suggestive of gastroduodenal irritation or ulcer. Severe pain should prompt workup with an upper gastrointestinal endoscopy. Serum amylase should be checked along with the routine blood (screening profile, creatinine, and CBC) in patients with abdominal pain. If an ulcer or gastroduodenitis is documented, therapy should be held for one month to allow healing. If abdominal pain is severe, the pump should be emptied of FUDR until results of workup are available.

If patients have delays in FUDR treatment, the cycle numbering will go as follows:

- 2 systemic treatments = 1 cycle
- If patients return for FUDR and the liver function tests (SGOT, alkaline phosphatase and/or bilirubin) are too elevated (as in table 1) patients will wait one to two weeks. If they are still elevated, patients will start the next cycle with systemic and not with FUDR. During that cycle if the liver function tests come down enough (according to Table Recommencing Treatment After Hold), patients will be able to receive FUDR again at a lower dose. In that case they can receive the FUDR, then two weeks later they will receive systemic once afterwards and then move onto the next cycle.
- If liver function tests are too high for a patient to receive FUDR, they may continue on study treatment with systemic chemotherapy for a total of 12 systemic treatments. In this case, the patient will be treated with systemic treatment on Day 1 and on Day 15, then move onto the next cycle starting with Day 1.

#### 11.4.3 Panitumumab Dose Modifications

- Infusion-Related Adverse Events: If a patient experiences an infusion-associated adverse event, premedication will be given for the next infusion; however, the infusion time may not be decreased. If the next infusion is well-tolerated with premedication, the subsequent infusion time may then be decreased by 30 + 10 minutes as long as the patient continues to be premedicated. If a patient experiences an infusion-associated adverse event with the 60-minute infusion, all subsequent doses should be given over 90 + 15 minutes. Similarly, if a patient experiences an infusion-associated adverse event with the 30-minute infusion, all subsequent doses should be given over 60 + 10 minutes.
- For subjects who experience toxicities while on study, one or more doses of panitumumab may need to be withheld, reduced, or delayed. On resolution of toxicity, a limited number of attempts to re-escalate reduced panitumumab doses will be allowed. Dose escalations above **6 mg/kg** starting dose are not allowed. Panitumumab dose reductions are listed in Table 1.

Symptomatic skin- or nail-related toxicity felt to be intolerable by the subject can have a reduction in dose according to Table 1.

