In the mCRC setting in combination with IFL (Study 20025409), the incidence of grade 3 or 4 diarrhea (58%) was notably higher than that historically expected for this already highly GI-toxic chemotherapy regimen, and 1 subject had an episode of grade 4 diarrhea that was also considered serious. Of note, panitumumab in combination with the FOLFIRI regimen using the same agents but different doses/infusion times was better tolerated with an incidence of grade 3 or 4 diarrhea similar to that expected from the literature for this chemotherapy regimen alone (25%) (Andre et al, 1999; Saltz et al, 2000). These data suggest that the potential for additive toxicities in the gastrointestinal tract exists when panitumumab is administered in combination with GI-toxic chemotherapy.

Acute renal failure has been observed in patients who develop severe diarrhea and dehydration.

Infusion reactions, including anaphylactic reactions, bronchospasm, and hypotension, have been reported in the clinical trials and post-marketing experience (including fatal outcomes). Fatal reactions have also been observed in patients with a history of prior hypersensitivity reaction to panitumumab including a case of fatal angioedema occurring more than 24 hours following the administration of panitumumab.

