##### Non-skin- or nail-related toxicities:

Any grade 3 or 4 toxicity with the following exceptions:

- Panitumumab will only be withheld for symptomatic hypomagnesemia and/or hypocalcemia that persists despite aggressive magnesium and/or calcium replacement
- Panitumumab will only be withheld for grade 3 or 4 nausea, diarrhea, or vomiting that persists despite maximum supportive care
- Panitumumab will only be withheld for grade  $\geq 3$  anemia or grade 4 thrombocytopenia that cannot be managed by transfusion(s) or cytokine therapy

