#### 11.4.5 Criteria for Re-treatment with Panitumumab

##### Skin- or nail-related toxicities:

Panitumumab administration may recommence once:

- The adverse event has improved to  $\leq$  Grade 2 or returned to baseline, or;
- The subject has recovered to the point where symptomatic skin- or nail-related toxicity is felt to be tolerable; or,

- Systemic steroids are no longer required, or
- IV antibiotic or IV antifungal treatment is no longer required

Non-skin- or nail-related toxicities:

Panitumumab administration may recommence once the adverse event has improved to  $\leq$  Grade 1 or returned to baseline.

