11.4.6 Dose Modification Schedule

- Subjects should be assessed for toxicity before each dose. Dose modification should be performed according to the schedule described below.
- Subjects who develop a toxicity that does not meet the criteria for withholding a dose of panitumumab (Section 11.4.4) should continue to receive panitumumab and their symptoms should be treated.
- Panitumumab-related toxicity will be considered resolved if it improves to a degree that allows for re-treatment with panitumumab (Section 11.4.5).

For subjects who experience a toxicity that meets the criteria for withholding a dose of panitumumab:

- Subjects receiving either 100% or 80% of the starting dose of panitumumab are allowed to have up to 2 subsequent doses withheld for toxicity. However a second dose should only be withheld if the toxicity has not resolved by the time that the subsequent dose is due.
- Subjects treated at the 100% dose level whose toxicity resolves after 1 dose of panitumumab is withheld should be re-started at the 100% dose level (recommended but not required, reduction to the 80% dose is allowed as an alternative to re-challenge with the 100% dose).
- If toxicity recurs, subjects treated at the 100% dose or 80% dose should be re-started at the 80% dose or 60% dose, respectively, when the toxicity resolves after withholding 1 or 2 doses of panitumumab.
- Subjects treated at the 100% dose level whose toxicity resolves only after 2 subsequent doses of panitumumab are withheld should be re-started at the 80% dose level.
- Subjects treated at the 80% dose level whose toxicity resolves after withholding 1 or 2 doses of panitumumab should be re-started at the 60% dose level.
- Subjects who experience toxicity at the 60% dose level will not be re-treated with panitumumab.

It is recommended that panitumumab doses will be escalated in subjects whose toxicity resolves to the degree that meets the criteria for re-starting a dose of panitumumab (Section 11.4.5). Dose escalations are recommended but not required. Dose escalations should occur in the following manner:

- Subjects treated at the 80% dose level whose toxicity does not recur should receive the 100% dose level at the next dose unless a previous attempt to re-escalate to the 100% dose level was not tolerated (re-initiation of the 80% dose is allowed as an alternative to dose escalation).

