- Subjects treated at the 60% dose level whose toxicity does not recur should receive the 80% dose at the next dose unless a previous attempt to re-escalate to the 80% dose level was not tolerated (re-initiation of the 60% dose is allowed as an alternative to dose escalation).

- Subjects who miss more than 2 consecutive scheduled doses due to toxicity or are unable to receive a dose of panitumumab within 6 weeks of having received their previous dose of panitumumab due to toxicity will be considered unable to tolerate panitumumab and will not be retreated with panitumumab.
- If a subject demonstrates a clinical benefit with a documented response of stable disease, partial response or complete response and there are reasons that the dose modification rules above cannot be implemented, the investigator should contact and discuss these reasons with Amgen. The investigator must obtain written agreement from Amgen before any changes in the dose modification rules can be implemented.

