#### 11.4.8 Discontinuation of Panitumumab

Panitumumab will be administered until subjects develop disease progression or are unable to tolerate panitumumab.

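### The panitumumab rules name no permanent stop after anaphylaxis or angioedema; re-exposure is left to a severity judgment with no threshold

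*Combined protocol and SAP*

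**What the plan says.** Several sections of the combined protocol and SAP bear on what happens after an infusion reaction to panitumumab.

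- **Section 11.2** stops the infusion for a serious reaction. For later doses: "Continuation of dosing will be based on the severity and resolution of the event". It gives no grade or type of reaction at which dosing ends. It also says that premedication may be used for later infusions.
- **Section 11.4.3**: "If a patient experiences an infusion-associated adverse event, premedication will be given for the next infusion". It then sets slower infusion times for later doses. The rule covers any infusion-associated adverse event.
- **Section 11.4.4** withholds panitumumab for non-skin toxicity under the rule "Any grade 3 or 4 toxicity with the following exceptions". The exceptions concern electrolytes, gastrointestinal toxicity, anemia and thrombocytopenia, not infusion reactions.
- **Section 11.4.5** allows non-skin toxicity to be re-treated once it is back to grade 1 or baseline.
- **Section 11.4.6** says of patients on the full dose that those "whose toxicity resolves after 1 dose of panitumumab is withheld should be re-started at the 100% dose level". It marks this as recommended but not required and allows 80% instead. It also says that patients whose toxicity does not meet the withholding criteria should go on receiving panitumumab.
- **The objective no-retreatment rules** in Section 11.4.6 are toxicity at the 60% dose level, more than two consecutive missed doses, or being "unable to receive a dose of panitumumab within 6 weeks of having received their previous dose of panitumumab due to toxicity".
- **Section 11.4.8**: "Panitumumab will be administered until subjects develop disease progression or are unable to tolerate panitumumab". Anaphylaxis, angioedema and hypersensitivity are not named.
- **Section 3.2.3**: "Fatal reactions have also been observed in patients with a history of prior hypersensitivity reaction to panitumumab". The same sentence includes a fatal angioedema with onset more than 24 hours after the dose.

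**The concern.** The protocol reports deaths in patients with earlier hypersensitivity to panitumumab, yet its dosing rules contain no matching stop. Section 6.2 excludes patients at entry for a history of allergic reactions to compounds similar to panitumumab. A patient who has such a reaction to panitumumab on study meets no equivalent written bar.

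Read literally, the dosing rules lean towards another dose. Section 11.4.3 describes how to give the next infusion, Section 11.4.5 opens the way to re-treatment on resolution, and Section 11.4.6 recommends full dose after one withheld dose. An angioedema graded below 3 would not meet the withholding criterion on grade, so the continuation sentence in Section 11.4.6 covers it. Nothing objective interrupts this sequence. The severity clause in Section 11.2 does, but without saying how severe is too severe.

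What is at stake is the safety of very few patients, not the efficacy result. These patients have completely resected disease, and panitumumab is the added drug under test. Without it they can still receive the Arm B regimen.

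**Working it through.** The plan states no figure on this point, so there is none to reproduce. The check has three parts.

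**1. Is there a named stop?** The sections on infusion reactions, withholding, re-treatment, dose modification, discontinuation and removal (3.2.2, 3.2.3, 5.6.5, 6.2, 11.2, 11.4.3 to 11.4.8, 13 and 17.2.2) were read for one. The only objective no-retreatment rules for panitumumab are the three in Section 11.4.6 listed above; Section 11.4.7 repeats the missed-dose and six-week limits. Other routes are general: inability to tolerate (11.4.8), toxicity not responding to dose modification (13.4) and investigator judgment (13.6, 17.2.2). None names anaphylaxis or angioedema.

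**2. Would the six-week rule stop re-exposure?** Panitumumab is given on days 15 and 29, and day 36 is day 1 of the next cycle (Section 4.1). With a 35-day cycle, dosing days are 15, 29, 15 + 35 = 50, 29 + 35 = 64, 85, and so on. The limit is 6 × 7 = 42 days.

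| Reaction on | Doses withheld | Next dose | Gap (days) | Beyond 42 days? |
|---|---|---|---|---|
| Day 15 | 0 (resolved before next dose) | Day 29 | 14 | No |
| Day 29 | 0 (resolved before next dose) | Day 50 | 21 | No |
| Day 15 | 1 | Day 50 | 35 | No |
| Day 29 | 1 | Day 64 | 35 | No |
| Day 15 | 2 | Day 64 | 49 | Yes |
| Day 29 | 2 | Day 85 | 56 | Yes |

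An acute reaction may well settle before the next dose is due. Re-exposure could then follow after as little as 14 days, or after 35 days if one dose is withheld. Neither gap triggers the six-week stop.

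**3. How many patients?** Inputs are 39 patients per arm (Section 14.0) and a severe infusion reaction rate *p*. Section 11.2 gives about 1%. Sections 3.2.2 and 3.2.3 say below 1%, so 0.5% is taken as an assumed lower value. Expected number = 39 × *p*; chance of at least one = 1 − (1 − *p*)^39.

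- *p* = 1%: 39 × 0.01 = 0.39; 1 − 0.99^39 = 0.324.
- *p* = 0.5% (assumed): 39 × 0.005 = 0.195; 1 − 0.995^39 = 0.178.

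These are chances of a first severe reaction, not of harm on re-exposure. The documents give no rate for the latter, and none for low-grade anaphylaxis or angioedema.

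**The case against.** The strongest reply is that Section 11.2 is the specific rule for serious reactions and already makes severity the criterion. On that reading, Section 11.2 decides whether dosing continues, and Section 11.4.3 only sets premedication and infusion time if it does. Sections 11.4.8, 13.4, 13.6 and 17.2.2 give further routes to stopping. Section 5.6.1 restricts panitumumab dosing to the direction of trial investigators. Sections 3.2.2 and 3.2.3 refer readers to the current Investigator's Brochure, which may hold rechallenge guidance.

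Most of this stands, and it rules out several stronger readings:

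- A reader might infer that the protocol compels full-dose rechallenge. It does not. Section 11.4.5 is permissive, the 100% restart is not required, 80% is allowed, and investigators may stop.
- A reader might take the 3% rate of potential reactions in Section 3.2.3 and get 1 − 0.97^39, about 70%, as the size of the problem. That rate rests on a broad definition; the version in Section 3.2.2 includes chills and fever. Premedication is a reasonable response to a mild event. The severe rate is the relevant one.
- A reader might cite FUDR at bilirubin 3.0 mg/dl or more (Section 11.4.2) as an absolute stop that panitumumab lacks. That stop is conditional: restart is allowed on disease progression with recovered bilirubin. The stop of 5FU for cardiac toxicity of grade 2 or higher (Section 11.4.1) is the closer parallel.

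The reply does not supply a threshold. A resolved anaphylaxis satisfies the resolution half of the Section 11.2 clause, and how much weight its severity carries is not stated. None of the infusion-reaction, restart or discontinuation rules points to the Brochure.

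**Conclusion.** The point holds as a gap in the written safety rules. Severity is mentioned but has no threshold, the later rules permit and partly favor another dose, and no section shown names a stop for the reactions that the protocol itself links to deaths.

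The size is about 0.2 to 0.4 expected severe reactions in Arm A, with an 18% to 32% chance of at least one. This assumes that rates from earlier panitumumab studies carry over to this combination and that 0.5% is a fair lower value. The efficacy result is not threatened.

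A reader might also conclude that every grade 3 or 4 infusion reaction must end panitumumab. The documents do not settle that: they give no data for choosing between grade 3 and grade 4. The supported conclusion is the narrower one, for anaphylaxis and angioedema. Whether a practical gap remains once the Brochure is read cannot be decided from these documents. This is a cheap improvement.

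**What to change.** 1. In Section 11.4.8, cross-referenced from Sections 11.2 and 11.4.3, add: *Panitumumab is permanently discontinued after anaphylaxis or angioedema of any grade, including onset more than 24 hours after a dose.*
2. State that the next-infusion rule in Section 11.4.3 and the continuation, restart and re-escalation rules in Sections 11.4.5 and 11.4.6 do not apply to these reactions.
3. State that these patients may continue hepatic arterial and systemic chemotherapy and stay in Arm A for 15-month RFS. Section 13 already continues follow-up for recurrence and survival after intolerable toxicity; this makes continued treatment and the analysis explicit.
4. Optionally, extend the stop to all grade 3 or 4 infusion reactions. This is for the sponsor to decide.

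The cost is one sentence and a few cross-references, with no change to sample size or analysis. The downside is that about 0 to 1 patient who might have tolerated rechallenge stops panitumumab. The any-grade wording could add slightly to that, but the documents give no rate for it.
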